8.5.2 Additional Safety Endpoints and Analyses

The incidence of all adverse events, other than those listed in ISO 11979-7:2018 tables E.3 and E.4, will be summarized with number and percentage by test and control eyes. 90% confidence intervals (showing both lower and upper 5% boundaries) will be provided for incidence. Data will be provided in line listings.

SPE analyses will be provided for control eyes for completeness.

The incidence of loss of 10 letters or more of BCDVA between any two postoperative visits will be summarized with number and percentage by test and control eyes. Data will be provided in line listings.

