4 STUDY OBJECTIVES

The purpose of this clinical study is to evaluate the safety and effectiveness of the PODEYE TORIC IOL. Objectives are based on ANSI Z80.30:2018)¹ and ISO 11979-7:2018)². More specifically, the purpose of this clinical study is to compare the visual outcomes and safety of the PODEYE TORIC IOL to that of the AcrySof monofocal non-toric IOL Model SA60AT³. The study is designed to meet the requirements specified for toric IOLs in ANSI Z80.30: 2018 standard.

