8 DATA ANALYSIS METHODS

8.1 DATA AND ANALYSIS CONVENTIONS

The following are some basic stipulations that, unless otherwise stated, apply by default throughout the plan.

- For the co-primary endpoints, the six-month postoperative visit (Form 4) will be the primary analysis time point unless otherwise noted. For the primary safety endpoints, the Form 4 visit will be the primary analysis time point.
- Monocular safety and effectiveness analyses will compare the test group and the control group.

- For all visual acuity-related endpoints in the study, best corrected distance visual acuity (BCDVA) and uncorrected distance visual acuity (UCDVA) are measured at 4 m using a ETDRS chart under photopic conditions. All postoperatively measured visual acuities are recorded and analyzed in logMAR for all endpoint analyses, summary statistics and calculations, and may be converted to Snellen equivalent values for tables, listings, and graphs.
- Safety data will not be imputed, although incomplete or missing dates may be imputed.
- Partial dates will be imputed for safety and effectiveness data, using the most conservative approach available; for safety data, dates will be imputed to result in the longest possible duration of a given adverse event; for effectiveness data, dates will be imputed to maximize the number of study days from the operative date.
- Partial dates in other contexts (e.g., medical history) will be imputed in a way to allow reasonable interpretation, such as to replace the missing date or the missing month with “1.” For example, a partial date recorded as “(missing date)/(missing month)/2020” will be imputed as “1/1/2020” and will be noted as “imputed” on any line listing.
- The expression “summary statistics” indicates sample size (N), mean, standard deviation (SD), median, minimum (Min), and maximum (Max) as applied to continuous variables, and indicates sample size (N), frequency and percent of relevant total as applied to categorical and some ordinal variables.
- All co-primary effectiveness and safety endpoints have to be met to claim overall effectiveness and safety success. Additional analyses and supportive analyses should not be used for the purpose of claims. Under this plan, type 1 error rates will be controlled at a significance level of 0.05 per individual hypothesis without adjustment for multiplicity.
- Data will be pooled across sites for overall analyses unless contraindicated by the poolability analysis in Section 7.8.1.

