A subject will be said to have experienced a persistent adverse event if a given adverse event is present at the conclusion of the clinical study (i.e., at database lock). The cumulative occurrence of an adverse event at an analytical time point refers to the total number of times a subject has experienced the occurrence of a given adverse effect between implantation and the conclusion of the clinical trial.

Incidence of adverse events (persistent or cumulative, as appropriate) listed in ISO 11979-7:2018 Table E.2 (Posterior chamber IOL adverse event rates will be compared to the historical control safety and performance endpoints (SPE) rates, as specified in **Section 7.5.1**. If none of the ISO-defined posterior chamber AE incidence rate is greater than the respective SPE rate, then investigational device will have met the co-primary safety endpoint on adverse event.

The AE tables will be listed by treatment group and will include the AE term, the event count, the incidence rate, and corresponding confidence intervals. The tables will be generated for the AEs listed in ISO 11979-7:2018, SAEs (separately for ocular and non-ocular), and all other AEs (separately for ocular and non-ocular). The table for the AEs listed in ISO 11979-7:2018 will also list *p*-values. The ocular AE tables may also be separately reported for device-related, procedure-related vs. non-related. If any UADE is reported in the study, they will be reported in a separate table.

Supplemental AE data listings will be ordered by subject and will list such information as AE term, treatment group, whether it is ocular or systemic, SAE (if applicable), date of onset, date of resolution, severity, relationship to the study device and relationship to the procedure. The onset of ocular adverse events will also be shown relative (in number of days) to the surgery date for that eye.

Per-subject data listings for death, SAEs, and premature discontinuation due to adverse events will also be produced.

Intraoperative adverse events are excluded from the above tables. An intraoperative AE is defined to be any adverse event with onset during surgery. Intraoperative adverse events will be presented in a data listing and summarized by treatment group.

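### The SAP promises a safety comparison with the control lens, but its legible methods give only by-arm summaries and no interval for the difference between arms.

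*SAP*

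**What the plan says.** **The promise.** SAP section 4 states that the study is to "compare the visual outcomes and safety of the PODEYE TORIC IOL to that of the AcrySof monofocal non-toric IOL"; Protocol 4.2 says the same. Among the default conventions in SAP 8.1 is: "Monocular safety and effectiveness analyses will compare the test group and the control group". Neither place names an estimator.

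**The legible methods.**

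- *ISO-listed events* (SAP 8.5.1): a one-sample exact binomial test of the test eyes against each SPE rate. For the other arm, SAP 8.5.2 adds only that "SPE analyses will be provided for control eyes for completeness".
- *SSIs related to the optical properties of the lens* (SAP 8.5.1): a one-sample 95% Clopper-Pearson interval. The total SSI rate is compared with its SPE rate.
- *Other adverse events* (SAP 8.5.2): these "will be summarized with number and percentage by test and control eyes", and "90% confidence intervals (showing both lower and upper 5% boundaries) will be provided for incidence".
- *Loss of 10 letters or more of BCDVA* (SAP 8.5.2): number and percentage by arm.
- *Adverse event tables* (SAP 8.5.3): by treatment group, these "will include the AE term, the event count, the incidence rate, and corresponding confidence intervals". No column for a difference is mentioned, and no confidence level is given there. P-values are confined to one table: "The table for the AEs listed in ISO 11979-7:2018 will also list" them. The only adverse event test described is the one against SPE rates.
- *Protocol 9.9*: the listed events against SPE limits, and other safety outcomes by count and percentage for each lens.

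Parts of Protocol 9.9, SAP 8.5.1 and the table list in SAP Appendix B are redacted.

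**The concern.** Randomization is 1:1 and stratified by site (Protocol 6.3). The control eyes are therefore the only reference group treated at the same sites, over the same period and from the same case mix. A fixed historical rate cannot by itself separate a shift caused by surgical technique or patient selection from an effect of the lens; the randomized difference can. For adverse events outside the ISO list no historical comparison is described, so the control arm is the only comparator.

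If the report shows two rates and two separate intervals, a reader who wants the promised comparison must judge the difference by eye. Comparing two one-arm intervals for overlap is a common shortcut and a poor substitute for an interval on the difference.

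**Working it through.** **1. Text check.** Each legible safety method was compared with the two statements of purpose. Every one is a by-arm summary or a one-sample test. No risk difference, risk ratio, between-arm interval or between-arm test for a safety outcome appears in the readable text.

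**2. The plan's own figures.** SAP 6.2 gives 115 eyes per arm and 13% attrition: 230 × (1 − 0.13) = 200.1, matching the stated 200. SAP 8.6 gives worst-case power 0.94 × 0.99 × 0.99 × 0.99 = 0.912, matching 91%. That figure covers the effectiveness endpoints only; no precision or power is stated for a between-arm safety comparison.

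**3. Worked example.** Assume 12 of 115 test eyes and 3 of 115 control eyes have an event. These counts are illustrative; the documents give no expected adverse event rates.

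- One-arm 90% Clopper-Pearson intervals: 6.1% to 16.4% and 0.7% to 6.6%. They overlap between 6.1% and 6.6%.
- Difference: 12/115 − 3/115 = 10.43% − 2.61% = 7.8 points.
- Newcombe 95% limits use the Wilson limits of each arm: 6.07% to 17.36% (test) and 0.89% to 7.39% (control).
 - Lower = 7.83 − √[(10.43 − 6.07)² + (7.39 − 2.61)²] = 7.83 − 6.47 = 1.4.
 - Upper = 7.83 + √[(17.36 − 10.43)² + (2.61 − 0.89)²] = 7.83 + 7.13 = 15.0.

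So the interval for the difference excludes zero although the separate intervals overlap. The example sits near the edge: with 13 versus 3 the separate 90% intervals no longer overlap (lower limit 6.8% against upper limit 6.6%). A second case, 14 versus 4, also overlaps (7.5% to 18.4% and 1.2% to 7.8%), with a difference of 8.7 points (95% CI 1.7 to 16.2).

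**4. How often the two readings differ.** Exact enumeration over two binomials, n = 115 per arm, assumed true rates:

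| Control vs test | Two 90% Clopper-Pearson intervals do not overlap | Newcombe 95% CI excludes 0 |
|---|---|---|
| 2% vs 2% | 0.2% | 2.0% |
| 5% vs 5% | 1.0% | 3.8% |
| 10% vs 10% | 1.2% | 4.4% |
| 2% vs 6% | 13.9% | 29.6% |
| 2% vs 10% | 54.6% | 73.5% |
| 5% vs 10% | 13.5% | 27.6% |
| 5% vs 15% | 52.1% | 71.9% |
| 10% vs 20% | 35.5% | 57.0% |

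**5. Is the 90% level to blame?** No. With equal standard errors, non-overlap of two 90% intervals acts like a two-sided test at 2 × [1 − Φ(1.645 × √2)] = 0.020. Two 95% intervals act like one at 2 × [1 − Φ(1.960 × √2)] = 0.006 and overlap still more often.

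**6. What the sample size allows.** By the normal approximation, a direct two-sided 5% comparison at 115 per arm reaches 80% power only at about 2% vs 11%, 5% vs 16% or 10% vs 24%. By exact enumeration, the overlap reading needs about 2% vs 13%, 5% vs 19% or 10% vs 27%.

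**The case against.** Several points on the other side stand.

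- A reader might infer that adverse events are reported only as one-arm 90% intervals. The documents do not support that: ISO-listed events have exact tests against SPE rates with p-values, and optical-property SSIs have a 95% interval. The 90% level is stated only in SAP 8.5.2.
- A reader might infer that the comparison is never estimated anywhere in the plan. That cannot be asserted: safety text and the table list are partly redacted, and redacted text is not absent. The crude difference can also be read off the by-arm rates; what is lacking in the legible text is its interval.
- A reader might take the overlap figures as the performance of the planned analysis. No section says overlap will be used to judge a difference. The figures illustrate a possible misreading.
- A reader might conclude that one-arm reporting is the main reason real differences would be missed. Sample size is the larger limit: for 5% vs 10%, the 95% interval for the difference excludes zero in only 27.6% of trials.
- The control arm is not ignored. It gets the same SPE analysis and side-by-side rates, so a rise in both arms would be visible.
- Co-primary safety success rests on SPE rates and on BCVA in test eyes, so nothing here changes that decision. SAP section 2 also allows additional analyses in the report.

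None of this supplies the missing piece. Two statements promise a comparison, and no legible section says how it is estimated or with what uncertainty. An analysis added after unmasking would leave the choice of outcomes and method open to selection. Rewording SAP 4 and 8.1 to say that safety is described by arm would remove the inconsistency, but would leave the randomized contrast unused.

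**Conclusion.** The point holds as a gap between stated purpose and legible method: safety is to be compared between the lenses, and no between-arm estimate with an interval is specified in the readable text. It affects interpretation of safety, not the success criteria, and merits a cheap correction before unmasking.

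Its size depends on assumed event rates. At 115 eyes per arm, and for the differing rates tabulated, a reader relying on overlap would see a signal about 14 to 21 percentage points less often than one given a 95% interval for the difference (for example 52.1% against 71.9% at 5% vs 15%). This rests on independent binomial counts, one eye per subject, all 115 eyes per arm contributing, and Clopper-Pearson limits for the one-arm intervals; SAP 8.5.2 does not name the interval method.

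**What to change.** In SAP 8.5.2 and 8.5.3, add a descriptive test-minus-control risk difference with a 95% Newcombe or Miettinen-Nurminen interval (choose one and name it) in the Safety population, for a fixed list:

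1. total SSI;
2. at least one cumulative event from ISO 11979-7:2018 Table E.2;
3. any ocular AE;
4. any ocular SAE;
5. BCDVA loss of 10 letters or more, among eyes with at least two postoperative BCDVA measurements.

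Item 2 is a new composite, so define it at eye level. Item 5 needs its own denominator because BCDVA is first measured postoperatively at Form 2. State that the intervals are not adjusted for multiplicity, are not hypothesis tests and leave the SPE criteria unchanged.

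The cost is SAP wording, two definitions and a small table or added column, with no new data. The downside is that an interval may exclude zero by chance: at a nominal 5% each, the chance for at least one of five is at most 5 × 5% = 25%, which is why the descriptive label matters.

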8.5.3 Adverse Event Reporting

The following definitions will characterize the nature of adverse events.

ADVERSE EVENT (AE)

An adverse event in this study is defined per ISO 14155:2020: Clinical investigation of medical devices for human subjects – Good clinical practice as any untoward medical occurrence, unintended disease or injury, or untoward clinical signs (including abnormal laboratory findings) in subjects, users or other persons, whether or not related to the investigational medical device. For this protocol, this definition includes events related to the comparator device(s) and/or the procedures involved.

ADVERSE DEVICE EFFECTS (ADE)

An adverse event related to the use of an investigational medical device or comparator device(s).

NOTE: This definition includes adverse events resulting from insufficient or inadequate instructions for use, deployment, implantation, installation, or operation; any malfunction; and use error or intentional misuse of the investigational or comparator(s) medical device.

DEVICE DEFICIENCY

Device deficiencies (ISO 14155:2020) related to the identity (e.g., labeling), quality, durability, reliability, safety, effectiveness, or performance of the study device must be reported to the Sponsor, or Sponsor's designee, within 7 days of the Investigator becoming aware of the deficiency. Device deficiencies must be recorded in the subject's case report form.

Device deficiencies will be categories as one of the following:

- **Device failure:** A device has failed if it is used according to the labeling, including without limitation, instructions for use, and applicable standards of medical practice but does not perform according to the labeling and negatively impacts the treatment.
- **Device malfunction:** A device malfunction is a change in the function of the device that is not described in the labeling and that may or may not affect device performance.

- **Device misuse:** A misused device, i.e., one that is not used by the Investigator (in the study) in compliance with applicable standards of medical practice, including without limitation, those described in the instructions for use and labeling, will not be considered a malfunction.
- **Other:** must be described by the Investigator

SERIOUS ADVERSE EVENT (SAE)

A serious adverse event (SAE) is defined as any untoward medical occurrence that meets any of the following:

- Requires inpatient hospitalization or prolongation of existing hospitalization;
- Requires medical or surgical intervention to preclude permanent impairment of a body function or permanent damage to a body structure;
- Is life threatening (places the subject at immediate risk of death from the event as it occurred) or sight threatening;
- Results in permanent impairment of a body function or permanent damage to a body structure;
- Results in death
- May jeopardize the subject and require medical or surgical intervention to prevent one of the other outcomes.

UNANTICIPATED ADVERSE DEVICE EFFECT (UADE)

An unanticipated adverse device effect is defined per 21CFR 812.3(s) as any serious adverse effect on health or safety or any life-threatening problem, or death caused by, or associated with, a device, if that effect, problem, or death was not previously identified in nature, severity, or degree of incidence in the protocol or supplementary plan such as Clinical Investigator's Brochure, or any other unanticipated serious problem associated with a device that relates to the rights, safety, or welfare of subjects. Per this definition, UADE will be a subset of the SAEs reported in the study. UADEs are reportable per 21 CFR 812.3(s).

An investigator shall submit to the sponsor and to the reviewing Institutional Review Board (IRB) a report of any unanticipated adverse device effect occurring during an investigation as soon as possible, but in no event later than 10 working days after the investigator first learns of the effect.

NOTE: Vision-threatening (sight-threatening) adverse events are considered an UADE, reportable per 21 CFR 812.3(s) and must be reported to sponsor.

GENERAL COUNTING METHODS

A subject will be said to have experienced the occurrence of a given adverse event if either a pre-existing condition has worsened and requires prescribed medical treatment after IOL implantation, or a previously non-existent condition has developed after IOL implantation and

this new condition is deemed to be a clinically untoward event. The same adverse event cannot occur more than once unless it resolves prior to occurring again. Each occurrence corresponds to a unique preferred term. Adverse event resolution is as specified on the Adverse Event Form.

A subject will be said to have experienced a persistent adverse event if a given adverse event is present at the conclusion of the clinical study (i.e., at database lock). The cumulative occurrence of an adverse event at an analytical time point refers to the total number of times a subject has experienced the occurrence of a given adverse effect between implantation and the conclusion of the clinical trial.

Incidence of adverse events (persistent or cumulative, as appropriate) listed in ISO 11979-7:2018 Table E.2 (Posterior chamber IOL adverse event rates will be compared to the historical control safety and performance endpoints (SPE) rates, as specified in **Section 7.5.1**. If none of the ISO-defined posterior chamber AE incidence rate is greater than the respective SPE rate, then investigational device will have met the co-primary safety endpoint on adverse event.

The AE tables will be listed by treatment group and will include the AE term, the event count, the incidence rate, and corresponding confidence intervals. The tables will be generated for the AEs listed in ISO 11979-7:2018, SAEs (separately for ocular and non-ocular), and all other AEs (separately for ocular and non-ocular). The table for the AEs listed in ISO 11979-7:2018 will also list *p*-values. The ocular AE tables may also be separately reported for device-related, procedure-related vs. non-related. If any UADE is reported in the study, they will be reported in a separate table.

Supplemental AE data listings will be ordered by subject and will list such information as AE term, treatment group, whether it is ocular or systemic, SAE (if applicable), date of onset, date of resolution, severity, relationship to the study device and relationship to the procedure. The onset of ocular adverse events will also be shown relative (in number of days) to the surgery date for that eye.

Per-subject data listings for death, SAEs, and premature discontinuation due to adverse events will also be produced.

Intraoperative adverse events are excluded from the above tables. An intraoperative AE is defined to be any adverse event with onset during surgery. Intraoperative adverse events will be presented in a data listing and summarized by treatment group.

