#### 8.7.3 DEFINITION OF ADVERSE DEVICE EFFECTS AND UNANTICIPATED ADVERSE DEVICE EFFECTS

An Adverse Device Effect (ADE) is any adverse event related to the use of a study device. This definition includes any events resulting from insufficient or inadequate instructions for use, deployment, implantation, installation or operation, or any malfunction of the device. This definition also includes any event resulting from use error or from intentional misuse of a study device.

An Unanticipated Adverse Device Effect (UADE) is any serious adverse effect on subject health or safety, or any life-threatening problem or death caused by or associated with the investigational device, if that effect, problem, or death was not previously identified in nature, severity, or degree of incidence in the study protocol.

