#### 8.7.6 EXPEDITED ADVERSE EVENT REPORTING

Any ocular SAE or UADE, whether the event is expected or unexpected, ***must be reported to the Sponsor, or the Sponsor's designee, within 24 hours*** of the Investigator becoming aware of the event. Non-ocular SAEs must be reported within 7 days.

SAEs and UADEs must be recorded in the subject's eCRF. Information provided on the eCRF should be supplemented with hospitalization records, death certificate, clinic notes from specialists evaluating the subject's condition, etc., as applicable for the event. The urgency for reporting SAEs/UADEs is 3-fold:

- To facilitate discussion [and implementation, if necessary] by the Sponsor and the Investigator of appropriate follow-up measures.
- To facilitate Investigator reporting of unanticipated problems involving risk to human subjects to the IRB, and
- To enable the Sponsor to fulfill the reporting requirements to the appropriate regulatory authority.

It is the responsibility of the Investigator to promptly notify the IRB of SAEs per the IRBs reporting requirements. Investigators must report the occurrence of a UADE to their reviewing IRB as soon as possible, but no later than 10 working days after first learning of the event. The Sponsor must report the results of an evaluation of an UADE to FDA and all reviewing IRBs and participating investigators within 10 working days after the Sponsor first receives notice of the effect.

---

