#### Postoperative Adverse Events

- Anterior uveitis (including iritis and iridocyclitis)
- Capsular block syndrome
- Choroidal detachment/hemorrhage
- Chronic anterior uveitis [anterior segment inflammation characterized by grade 1+ cell or greater (using the Standardization of Uveitis Nomenclature [SUN] criteria) that is persistent for greater than 3 months after surgery, or relapses in less than 3 months after discontinuation of therapy, or the subject is maintained on therapy for more than 3 months to control inflammation.] Note that any iritis present at the final visit is considered significant and should be counted as a 'persistent ISO SPE event'.
- Visually significant corneal edema [corneal swelling (stromal or epithelial) resulting in BCDVA of 0.3 logMAR or worse at Form 3 or later]. Note that any corneal stromal edema present at the final visit is considered significant and should be counted as a 'persistent ISO SPE event'.
- Clinically significant cystoid macular edema (CME) diagnosed by clinical exam and adjunct testing (e.g., OCT or other method), resulting in BCDVA of  $\leq 0.3$  logMAR at Form 3 or later
- Endophthalmitis (intraocular inflammation leading to diagnostic vitreous tap and use of intraocular antibiotics)
- Flat anterior chamber with lens/cornea touch or a shallow chamber with iridocorneal apposition without lens/cornea touch
- Anterior Capsular Contraction Syndrome (ACCS, Phimosis)
- Hypopyon
- Corneal endothelial damage
- Incorrect IOL power resulting in secondary surgical intervention
- Increased IOP (elevation of IOP  $\geq 10$  mmHg above the IOP measured at the Preoperative Visit to a minimum of 25 mmHg)
- Infectious keratitis
- IOL damage resulting in secondary surgical intervention

- IOL dislocation, tilt, decentration, luxation, rotation resulting in secondary surgical intervention
- Best-corrected distance visual acuity loss of 2 lines (10 letters) or more on the ETDRS chart measured at or after postoperative Form 4 compared to any prior postoperative visit
- Best-corrected distance visual acuity loss of 2 lines (10 letters) or more since the prior visit
- Mechanical pupillary block (A shallowing of the anterior chamber due to obstruction of aqueous humor flow from the posterior to anterior chamber through the pupil by the crystalline lens, vitreous face, or implanted device)

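### A note in SAP 8.5.3 makes every sight-threatening adverse event a UADE, contradicting the SAP's own definition and protocol 8.7.3

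*SAP*

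**What the plan says.** SAP 8.5.3 defines a UADE as a serious effect, life-threatening problem or death that is caused by or associated with a device, and it counts the effect only "if that effect, problem, or death was not previously identified in nature, severity, or degree of incidence in the protocol" or in a supplementary plan such as the investigator's brochure. A further limb covers any other unanticipated serious device-associated problem bearing on subjects' rights, safety or welfare. The SAP then remarks: "Per this definition, UADE will be a subset of the SAEs reported in the study". After a sentence on reporting times it adds: "NOTE: Vision-threatening (sight-threatening) adverse events are considered an UADE, reportable per 21 CFR 812.3(s) and must be reported to sponsor".

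Protocol 8.7.3 has the same test, "if that effect, problem, or death was not previously identified in nature, severity, or degree of incidence in the study protocol". It ties the effect to the investigational device and has no such note.

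Both documents list sight threat among the SAE criteria (protocol 8.7.2, SAP 8.5.3). Protocol 8.7.7 names anticipated postoperative events, among them "Endophthalmitis (intraocular inflammation leading to diagnostic vitreous tap and use of intraocular antibiotics") and rhegmatogenous retinal detachment. Both conditions also appear among the known risks in protocol 2.3.1 and the cumulative events in 8.7.2.1.

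On output, SAP 8.5.3 says: "If any UADE is reported in the study, they will be reported in a separate table".

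**The concern.** The note uses the term adverse event, which SAP 8.5.3 defines to include events "whether or not related to the investigational medical device". Taken literally, it drops two conditions that the definition requires: association with a device, and not having been identified beforehand. An endophthalmitis of the kind the protocol foresees would then be tabulated as an unanticipated device effect. So would a sight-threatening event that has nothing to do with either lens, or one in an eye with the marketed control lens.

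At stake is the meaning of the UADE table. A reader of the study report will take an entry there as a serious device effect that nobody had foreseen. If the table also holds foreseen complications of cataract surgery, the count no longer measures that.

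**Working it through.** The plan states no figure for this point, so the check sets the rules side by side.

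**Conditions for UADE status**

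| Condition | SAP 8.5.3 definition | Protocol 8.7.3 | SAP 8.5.3 note |
|---|---|---|---|
| Serious | required | required (or a life-threatening problem or death) | met through the sight-threat SAE criterion |
| Device association | required, any device | required, investigational device | not required |
| Not previously identified | protocol or supplementary plan | study protocol | not required |

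The SAP also has the limb for other unanticipated serious device-associated problems, which likewise requires both device association and unexpectedness.

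**Three test cases**

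1. *Sight-threatening endophthalmitis in a test eye, of the nature, severity and incidence already identified.* Both definitions: not a UADE. Note: UADE.
2. *Sight-threatening retinal detachment judged unrelated to any device.* Both definitions: not a UADE. Note: UADE.
3. *Sight-threatening event in a control eye, associated with the control lens and already identified.* Protocol 8.7.3: not a UADE, because the lens is not the investigational device. SAP definition: not a UADE, because it was identified. Note: UADE.

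**Can the subset sentence reconcile them?** No. Sight-threatening events are SAEs, so the note keeps UADEs within the SAEs. The difficulty is that it admits SAEs failing the other two tests.

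**Does the exclusion of intraoperative events remove the problem?** No. SAP 8.5.3 excludes them from its adverse event tables, but endophthalmitis and rhegmatogenous retinal detachment are on the protocol's postoperative list.

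**Size.** The documents give no rate of sight-threatening but identified events. For scale only, assume a rate r per eye, independent across the 230 eyes (one per subject). The expected number is 230 × r, and the chance of at least one is 1 − (1 − r)^230.

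- r = 0.5%: 230 × 0.005 = 1.15; 1 − 0.995^230 = 0.68
- r = 1%: 230 × 0.01 = 2.3; 1 − 0.99^230 = 0.90
- r = 2%: 230 × 0.02 = 4.6; 1 − 0.98^230 = 0.99

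These rates are assumptions without an anchor in the documents. The results show only that a handful of events would be enough for the two rules to give different tables.

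**Notification times.** SAP 8.5.3 gives the investigator an outer limit of 10 working days for reporting a UADE to both the sponsor and the IRB. Protocol 8.7.6 sets 24 hours to the sponsor for any ocular SAE or UADE and uses the longer limit for the IRB: "Investigators must report the occurrence of a UADE to their reviewing IRB as soon as possible, but no later than 10 working days". The IRB limits agree; the sponsor limits do not.

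**The case against.** The strongest reply is that the note has little practical reach.

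- *Reporting.* A reader might infer that it triggers extra reports to FDA, all IRBs and all investigators. The documents do not support that. SAP section 2 lets the SAP supersede the protocol only for statistical analysis methods, and protocol 10.1.8 binds investigators to the protocol, whose UADE definition has no such note. This objection stands.
- *The table.* SAP 8.5.3 speaks of UADEs reported in the study, investigators record seriousness and expectedness for each event (protocol 8.7.5), and no SAP text tells the statistician to reclassify events. This stands in part: the note may never be applied. It is nevertheless a classification rule in the section that governs the table, and a programmer could follow it.
- *A hidden signal.* A reader might infer that a genuine UADE would be lost among known complications. That is unlikely, because SAP 8.5.3 also requires subject-level listings with event term, treatment group, severity, and relationship to device and procedure.
- *A true count of zero.* A reader might infer that no listed event can be a UADE. Both definitions say otherwise: unidentified severity or degree of incidence is enough, and protocol 8.7.7 gives no incidences.
- *Two conflicting tables.* Protocol 9.9 mentions an anticipated/unanticipated tabulation, but SAP 8.5.3 does not repeat it and the table list in SAP Appendix B is redacted. It cannot be confirmed that one event would appear under both labels.
- *Timing.* The SAP limit is an outer one, and reporting within 24 hours satisfies both texts. This is true, but a reader of the SAP alone would not learn of the 24-hour requirement.

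The protocol does not itself call endophthalmitis or retinal detachment sight-threatening. That is a clinical reading, though a plain one.

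**Conclusion.** The contradiction is real and can be seen within SAP 8.5.3 alone, as well as against protocol 8.7.3 and 8.7.7. If the note is applied in the analysis, the UADE table will include sight-threatening events that fail the UADE definition, among them foreseen complications, unrelated events and control-arm events. How many cannot be derived from the documents.

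The effect is confined to that classification and table. The co-primary safety endpoints in SAP 8.5.1 (SSIs, ISO adverse event rates, BCVA) do not use the UADE count, so no test, population or success criterion changes. An effect on site or FDA reporting is possible only if the SAP text is followed over the protocol. The conclusion rests on the literal wording of the note and on reading events such as endophthalmitis as capable of threatening sight. The assumed rates play no part in it.

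**What to change.** Delete the note. Alternatively, restate it to say that sight-threatening adverse events are SAEs, are reported under protocol 8.7.6, and enter the UADE table only if they meet the full UADE definition already in SAP 8.5.3. That means serious, device-associated, and not previously identified in nature, severity or degree of incidence anywhere in the protocol or supplementary plan, or another unanticipated serious device-associated problem.

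Do not narrow the test to the list in protocol 8.7.7. Section 2.3.1 identifies further risks, and it names lens dislocation without the condition in 8.7.7 that it led to secondary surgery.

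Reconcile the SAP's outer limit for notifying the sponsor with protocol 8.7.6, for example by replacing it with a cross-reference.

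The cost is a few lines of SAP text, with no change to data or procedures. No notification is lost, because protocol 8.7.6 already sends every ocular SAE to the sponsor within 24 hours, expected or not.
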